13.2.1 Definition of source data

All source documents must be accurate, clear, unambiguous, permanent, and capable of being audited. They should be made using some permanent form of recording (ink, typing, printing, optical disc). They should not be obscured by correction fluid or have temporary attachments (such as removable self-stick notes). Photocopies of CRFs are not considered acceptable source documents.

Source documents are original records in which raw data are first recorded. These may include hospital/clinic/general practitioner records, charts, diaries, x-rays, laboratory results, printouts, pharmacy records, care records, ECG or other printouts, completed scales, or quality of life questionnaires, for example. Source documents should be kept in a secure, limited access area.

Source documents that are computer generated and stored electronically must be printed for review by the monitor (eg, ECG reports). Once printed, these copies should be signed and dated by the investigator and become a permanent part of the subject's source documents. The investigator will facilitate the process for enabling the monitor to compare the content of the printout and the data stored in the computer to ensure all data are consistent.

Electronic data records, such as Holter monitor records or electroencephalogram records, must be saved and stored as instructed by UCB (or designee).

13.2.2 Source data verification

Source data verification ensures accuracy and credibility of the data obtained. During monitoring visits, reported data are reviewed with regard to being accurate, complete, and verifiable from source documents (eg, subject files, recordings from automated instruments, tracings [ECG], x-ray films, laboratory notes). All data reported on the eCRF should be supported by source documents, unless otherwise specified in Section 13.2.1.

13.3 Data handling

13.3.1 Case Report form completion

The study will be performed using electronic data capture (EDC). The investigator is responsible for prompt reporting of accurate, complete, and legible data in the eCRFs and in all required reports.

Any change or correction to the eCRF after saving must be accompanied by a reason for the change.

Corrections made after the investigator's review and approval (by means of a password/electronic signature) will be reapproved by the investigator.

The investigator should maintain a list of personnel authorized to enter data into the eCRF.

Detailed instructions will be provided in the eCRF Completion Guidelines.

13.3.2 Database entry and reconciliation

Case Report forms/external electronic data will be entered/loaded into a validated electronic database using a clinical data management system (CDMS). Computerized data cleaning checks will be used in addition to manual review to check for discrepancies and to ensure consistency of the data. In the EDC system, the data are entered into the eCRFs once by the designated site personnel and are subsequently verified.

An electronic audit trail system will be maintained within the CDMS to track all data changes in the database once the data have been saved initially into the system or electronically loaded. Regular backups of the electronic data will be performed.

13.3.3 Subject Screening and Enrollment log/Subject Identification Code list

The subject's screening and enrollment will be recorded in the Subject Screening and Enrollment Log.

The investigator will keep a Subject Identification Code list. This list remains with the investigator and is used for unambiguous identification of each subject.

The subject's consent and enrollment in the study must be recorded in the subject's medical record. These data should identify the study and document the dates of the subject's participation.

13.4 Termination of the study

UCB reserves the right to temporarily suspend or prematurely discontinue this study either at a single site, multiple sites, or at all sites at any time for reasons including, but not limited to, safety or ethical issues, inaccurate or incomplete data recording, noncompliance, or unsatisfactory enrollment with respect to quality or quantity.

If the study is prematurely terminated or suspended, UCB (or its representative) will inform the investigators/institutions and the regulatory authority(ies) of the termination or suspension and the reason(s) for the termination or suspension, in accordance with applicable regulatory requirement(s). The IRB/IEC should also be informed and provided with reason(s) for the termination or suspension by the sponsor or by the investigator/institution, as specified by the applicable regulatory requirement(s). In addition, arrangements will be made for the return of all unused IMP and other material in accordance with UCB procedures for the study.

13.5 Archiving and data retention

The investigator will maintain adequate records for the study, including eCRFs, medical records, laboratory results, Informed Consent documents, drug dispensing and disposition records, safety reports, information regarding participants who discontinued, and other pertinent data.

All essential documents are to be retained by the investigator until at least 2 years after the last approval of a marketing application in an ICH region and until there are no pending or contemplated marketing applications in an ICH region, or at least 2 years have elapsed since the formal discontinuation of clinical development of the IMP. These documents should be retained for a longer period, however, if required by the applicable regulatory requirement(s) or by an

agreement with UCB (CPMP/ICH/135/95, 2002 [Section 4.9.5]). The investigator will contact UCB for authorization prior to the destruction of any study records or in the event of accidental loss or destruction of any study records. The investigator will also notify UCB should he/she Audit and inspection

The investigator will permit study-related audits mandated by UCB, after reasonable notice, and inspections by domestic or foreign regulatory authorities.

The main purposes of an audit or inspection are to confirm of study-related have been professionally.

study procedures) are appropriate for the study, and that all data relevant for the evaluation of the IMP have been processed and reported in compliance with the planned arrangements, the protocol, investigational site, and IRB/IEC SOPs, ICH-GCP, and applicable regulatory requirements.

The investigator will provide direct access to all study documents, source records, and source data. If an inspection by a regulatory authority is announced, the investigator will immediately inform UCB (or designee).

13.7 **Good Clinical Practice**

Noncompliance with the protocol, ICH-GCP, or local regulatory requirements by the investigator, institution, institution staff, or designees of the sponsor will lead to prompt action by UCB to secure compliance. Continued noncompliance may result in the termination of the site's involvement in the study.

14 STATISTICS

A description of statistical methods follows and will be described in more detail in the Statistical Analysis Plan (SAP). Deviations from the SAP will be documented in the Clinical Study Report.

Definition of analysis sets 14.1

Enrolled Set (ES):

The ES will consist of all subjects who have given informed consent.

Safety Set (SS):

The SS will consist of all subjects who have received at least 1 infusion (full or partial infusion) of IMP and will be used for the demographics and analysis of safety data.

Full Analysis Set (FAS):

The FAS will consist of all subjects who have received at least 1 infusion (full infusion) of IMP and, in addition, have a Baseline and at least 1 post-Baseline measurement for platelet count.

The analysis of the PD (excluding total IgG, and IgG subclasses), efficacy, and immunologic variables will be performed on the FAS. Selected outputs may be repeated for the PD Per Protocol Set (PD-PPS). Further details will be provided in the SAP.

Per Protocol Set:

The PPS is a subset of the FAS, consisting of those subjects who had received all foreseen sc infusions, had a platelet count measurement during the Observation Period, and no important protocol deviations that may potentially affect the platelet count as confirmed during a pre-analysis review of the data prior to database lock. Protocol deviations may not necessarily lead to total exclusion of a subject from the PPS but may lead to exclusion of specific data.

Pharmacokinetic Per Protocol Set (PK-PPS):

The PK-PPS is a subset of the FAS, consisting of those subjects who had no important protocol deviations potentially affecting the plasma concentration of UCB7665, as confirmed during a pre-analysis review of the data prior to database lock. Protocol deviations may not necessarily lead to total exclusion of a subject from the PK-PPS but may lead to exclusion of specific data.

Pharmacodynamic Per Protocol Set (PD-PPS)

The PD-PPS is a subset of the FAS, consisting of those subjects who had no important protocol deviations potentially affecting the serum concentration of total IgG, as confirmed during a pre-analysis review of the data prior to database lock. Protocol deviations may not necessarily lead to total exclusion of a subject from the PD-PPS but may lead to exclusion of specific data.

The PD-PPS will be used for the analysis of the total IgG, and IgG subclasses.

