7.2 Treatment to be administered

Subjects in Dose Arm 1 will receive 5 sc doses of UCB7665 4mg/kg at 1-week intervals.

Subjects in Dose Arm 2 will receive 3 sc doses of UCB7665 7mg/kg at 1-week intervals.

Subjects in Dose Arm 3 will receive 2 sc doses of UCB7665 10mg/kg at a 1-week interval.

Subjects in Dose Arm 4 will receive 1 sc dose of UCB7665 15mg/kg.

Subjects in Dose Arm 5 will receive 1 sc dose of UCB7665 20mg/kg.

The IMP will be administered as a sc infusion using an infusion pump:

The perfusor will be programmed at a constant flow rate of 20mL/h for all subjects. In the case of any blockage of the infusion, a suitable flush (eg, 0.9% sodium chloride) is allowed.

The subject's body weight at Screening Visit will be used for the dose calculation. The dose will be constant for a subject throughout the duration of the study, and will not be adjusted during the treatment.

The exact procedure for dose preparation according to dose arm and body weight will be provided in a pharmacy manual.

The infusion rate may be reduced at any time at the discretion of the investigator. If an infusion is interrupted, it can be restarted if the investigator considers it appropriate to do so. The chronology of these events should be recorded accurately in the source data and eCRF.

In the event of a severe infusion reaction, the subject must permanently discontinue IMP (see Section 12.1.10).

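### Section 14.1 removes treated subjects who never complete an infusion from every non-safety set, assigns the secondary IgG objective only to a deviation-selected set, and leaves the platelet-based PPS without a stated use

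*Protocol*

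**What the plan says.** Section 14.1 sets two different exposure rules. The Safety Set takes "all subjects who have received at least 1 infusion (full or partial infusion) of IMP". The FAS takes only "all subjects who have received at least 1 infusion (full infusion) of IMP", and a Baseline and at least one post-Baseline platelet count are also needed. The PPS, PK-PPS and PD-PPS are each defined as subsets of the FAS.

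The assignment of analyses follows: "The analysis of the PD (excluding total IgG, and IgG subclasses), efficacy, and immunologic variables will be performed on the FAS". For the excluded IgG variables, "The PD-PPS will be used for the analysis of the total IgG, and IgG subclasses". The PD-PPS selects on important deviations that could affect total IgG. The PPS selects on receipt of every planned infusion, a platelet count in the Observation Period, and absence of deviations that could affect the platelet count. No sentence in Sections 14.1 to 14.8 gives the PPS an analysis. The only repeat analysis mentioned is this: "Selected outputs may be repeated for the PD Per Protocol Set (PD-PPS). Further details will be provided in the SAP".

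Other sections bear on who can be lost. Section 7.2 states: "In the event of a severe infusion reaction, the subject must permanently discontinue IMP". Section 12.1.10 has the infusion stopped at once in that case. Section 5.1 gives Dose Arms 4 and 5 one dose each, with 6 to 12 subjects per arm. Section 6.4.1 says withdrawn subjects are not replaced but are encouraged to keep attending Observation Period visits. Section 3.2 lists change in total IgG as a secondary objective, and Section 14.8 gives exploration of IgG reduction as one reason why 6 to 12 subjects suffice in Dose Arms 3 to 5.

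**The concern.** Three features of Section 14.1 pull in the same direction.

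- **Exposure rule.** Whether a subject completes an infusion can depend on how the drug is tolerated. A set that requires a completed infusion then selects on an early effect of treatment. Such a subject may well attend the later visits, so platelet and IgG data would be collected and left out of the analysis.
- **IgG.** The protocol provides no analysis of total IgG in all treated subjects with data. The PD evidence, which is part of the case for the size of Dose Arms 3 to 5, rests on a set chosen by deviations arising after treatment starts.
- **Per-protocol sets.** The set built for platelet questions has no stated role. The only set named for repeats is built for IgG questions.

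At stake are the description of efficacy and PD effect by dose arm, and above all the small single-dose arms, where one subject is a large share of the denominator. The primary safety analysis is not affected.

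**Working it through.** **The plan's own figure.** Section 14.8 claims power above 80% to confirm a true 50% response rate against 15% with 15 subjects. It states no significance level for this claim; I carried over the 1-sided 5% given for the t-test. Exact binomial:
- P(X ≥ 5 | 15, 0.15) = 0.062, above 5%; P(X ≥ 6 | 15, 0.15) = 0.017, so at least 6 responders are needed.
- P(X ≥ 6 | 15, 0.50) = 0.849. The stated figure reproduces.

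If 1 or 2 subjects leave the set, the cut-off falls to 5 and exact power is 0.910 (n = 14) or 0.867 (n = 13), still above 80%. For the t-test the protocol gives no SD. A difference of 100 − 25 = 75 (×10⁹/L) with 80% power at n = 15 implies an SD of about 111, and power would be about 77% at n = 14 and 74% at n = 13. Admitting partial infusions changes no planned sample size, significance level or power.

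**Who is lost under the FAS rule.**

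| Case | Safety Set | FAS and its subsets |
|---|---|---|
| Arms 1 to 3: partial first infusion, full later one | in | not excluded by the exposure rule |
| Any arm: infusion interrupted, restarted and completed (Section 7.2 allows restart) | in | not excluded by the exposure rule |
| Arms 1 to 3: first infusion stopped, IMP permanently discontinued | in | out |
| Arms 4 and 5: the only infusion stopped and not completed | in | out |

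**Effect on a response rate.** With k responders among N treated and e excluded non-responders, the rate moves from k/N to k/(N − e).

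| Arm size | All treated | e = 1 | e = 2 |
|---|---|---|---|
| 6 | 2/6 = 33.3% | 2/5 = 40.0% | 2/4 = 50.0% |
| 6 | 3/6 = 50.0% | 3/5 = 60.0% | 3/4 = 75.0% |
| 12 | 6/12 = 50.0% | 6/11 = 54.5% | 6/10 = 60.0% |
| 15 | 6/15 = 40.0% | 6/14 = 42.9% | 6/13 = 46.2% |
| 15 | 7/15 = 46.7% | 7/14 = 50.0% | 7/13 = 53.8% |

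The upward direction depends on the excluded subject being a non-responder. If the one excluded subject were a responder, 2/6 (33.3%) would become 1/5 (20.0%).

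**How likely a loss is.** The protocol gives no rate of incomplete infusions. Assume a chance q per subject of never completing one. The chance of losing at least one subject is 1 − (1 − q)^N.

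| q (assumed) | N = 6 | N = 12 | N = 15 |
|---|---|---|---|
| 2% | 11% | 22% | 26% |
| 5% | 26% | 46% | 54% |
| 10% | 47% | 72% | 79% |

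**IgG and the per-protocol sets.** No arithmetic applies. Side by side, Section 3.2 makes total IgG a secondary objective, the FAS assignment expressly leaves it out, and only the PD-PPS receives it. The PPS and PD-PPS criteria also differ in practice. A TPO-R agonist is prohibited under Section 7.8.2 and bears on the platelet count, yet nothing in the PD-PPS definition is aimed at it.

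**The case against.** The other side has several fair points, and each limits the concern.

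- A reader might infer that everyone with an incomplete first infusion is dropped. The text does not say so: one full infusion at any visit is enough, and an interrupted infusion may be restarted. Only subjects who never complete any infusion are lost.
- A reader might infer that platelet outputs will be checked on the PD-PPS and that the PPS is never used. The repeat sentence is optional, names no outputs and defers details to the SAP, which is not at hand. What is shown is that this protocol states no use for the PPS and names only the PD-PPS for repeats.
- A reader might infer that deviation-based exclusions raise the response rates. They do not, because response is analysed on the FAS, which has no deviation criterion.
- For IgG, the direction of any bias is not established. IVIg and plasma exchange, both prohibited, directly alter serum IgG, so a set that removes affected values has a legitimate purpose. The PD-PPS does not require all infusions and may drop individual values rather than whole subjects.
- The trial is uncontrolled, safety is primary, dose-arm decisions rest on safety data, the IgG analysis is descriptive, and all data will be listed.

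These points narrow the scope and temper the urgency. They do not remove the core. The FAS exposure rule and the IgG assignment are fixed in Section 14.1, so a SAP could repair them only by departing from the protocol.

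**Conclusion.** The concern holds in this form: Section 14.1 excludes treated subjects with no completed infusion from all non-safety sets; it gives total IgG and its subclasses no analysis outside the PD-PPS; and it leaves the PPS without a stated use while the IgG-based PD-PPS is the only set named for repeats. The first part matters most in Dose Arms 4 and 5, where one infusion is the whole treatment.

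The size is illustrative. One excluded non-responder adds about 7 points in an arm of 6 (33% to 40%) and about 3 points in an arm of 15 (40% to 43%). This assumes that at least one subject completes no infusion, has the required counts, and is a non-responder; the protocol gives no rate for any of these. No effect has been quantified for the main efficacy variable, the maximum platelet increase, or for IgG. Planned sample size and power are unchanged.

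**What to change.** Amend Section 14.1 in three places:

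1. Define the FAS as subjects with any full or partial infusion, a Baseline platelet count and at least one post-Baseline platelet count.
2. Analyse total IgG and IgG subclasses on the FAS, with the PD-PPS as the supportive analysis.
3. Name the PPS, not the PD-PPS, for any repeat of platelet outputs.

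The handling of subjects without a post-Baseline count can stay with the SAP, as Section 14.6 provides. The rules for stopping or restarting an infusion need no change for this purpose. The cost is a short wording change, a few extra tables, and possibly slightly less favourable rates.

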14.2 General statistical considerations

All analyses will be performed using SAS® version 9.2 or later (SAS Institute, Cary, NC, USA). Continuous variables will be summarized by visit (where applicable) with the statistics including the number of subjects (n), mean, standard deviation (SD), median, minimum, and maximum. Categorical variables will be summarized by visit (where applicable) with frequency counts and percentages. Analyses will be performed by dose arm, unless otherwise stated. In the event that the number of planned infusions in the dose arms are modified following review by the DMC, the data will be summarized based on the actual dose arms completing the study. For example, if the weekly 5x4mg/kg dose arm is modified such that some subjects receive only 4 infusions, then the data will be summarized separately for this new dose regimen.

Data listings containing all documented data and all calculated data will be generated.

Baseline will be the last non-missing data collected prior to the first dose of IMP, and measurement-specific Baseline values will be defined in the SAP.

14.3 Rianned safety analyses

14.3.1 Analysis of the primary safety variable

All AEs will be coded using the Medical Dictionary for Regulatory Activities[®] (MedDRA[®]). The incidence of subjects with TEAEs will be determined and presented by dose arm and overall.

Only TEAEs will be included in the summary tables. As an additional analysis, the incidence of subjects with TEAEs will be determined and presented separately for the Dosing Period and the Observation Period by dose arm and overall.

Adverse events starting before time of IMP administration or after 8 weeks after the final dose will be listed only.

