4 STUDY VARIABLES

4.1 Primary variable

The primary safety variable is:

• Occurrence of TEAEs

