subjects experiencing severe headaches or GI disturbances (only in case of Adverse Events of Interest, see Section 12.4)

- Serum BAFF levels
- Exploratory biomarker analysis
- Serum total IgG and IgG subclasses concentration
- Serum IgA, IgM, and IgE concentration
- Serum cytokines only in case of late infusion reactions visible during the visit
- Headache questionnaire, only if subject experiences severe headaches, followed by a neurological assessment (including fundoscopy). Additionally, other diagnostic procedures including but not limited to CT scan, MRI and/or LP for CSF collection to be performed if indicated at the discretion of the investigator, considering the local guidelines for performing LP in subjects with ITP.

End-of-Study Visit: Visit 15 (Week 13/Day 85) [UCB7665 4mg/kg]/ 8.4.8 Visit 13 (Week 11/Day 71) [UCB7665 7mg/kg]/ Visit 12 (Week 10/Day 64) [UCB7665 10mg/kg] Visit 10 (Week 9/Day 57) [UCB7665 15mg/kg and UCB7665 20mg/kg]

25 Of Variations thereof The End-of-Study Visit will be conducted 8 weeks after the final dose. A visit window of ±2 days is applicable for this visit relative to the day of the final dosing visit. The following assessments will be performed at this visit:

- Concomitant medications
- Concomitant medical procedures
- Vital signs (systolic and diastolic blood pressure, pulse rate, temperature, and respiratory

- Physical examination (complete)

 12-lead ECG (triplicate)

 Urine pregnancy test for women of childbearing potential

 Urine sample for urinalysis

 Blood sample for the following:

 Standard safety laboratories: hematology including coagulation parameters, clinical chemistry chemistry
 - Anti-UCB7665 antibodies
 - Serum total IgG and IgG subclasses concentration
 - ITP-specific autoantibodies
- For all dose arms, collection of whole blood for exploratory RNA analyses
- ITP bleeding scale
- **NFI-MS**
- Subject exit interview
- Serum cytokines, only in case of late infusion reactions visible during the visit
- Headache questionnaire, only if subject experiences severe headaches, followed by a neurological assessment (including fundoscopy). Additionally, other diagnostic procedures including but not limited to CT scan, MRI and/or LP for CSF collection to be performed if indicated at the discretion of the investigator, considering the local guidelines for performing LP in subjects with ITP.
- TB signs and symptoms questionnaire

8.5 **Early Withdrawal Visit**

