In order to ensure complete safety data collection, all AEs occurring during the study (ie, after the signing of the Informed Consent form), including any pretreatment and posttreatment periods required by the protocol, must be reported in the eCRF even if no IMP was taken but specific study procedures were conducted. This includes all AEs not present prior to the initial visit and all AEs that recurred or worsened after the initial visit.

Signs or symptoms of the condition/disease for which the IMP is being studied should be recorded as AEs only if their nature changes considerably or their frequency or intensity

Confidential

Page 92 of 353

increases in a clinically significant manner as compared to the clinical profile known to the investigator from the subject's history or the Baseline Period.

Treatment-emergent AEs are defined as AEs starting after the time of first IMP administration up to and including 8 weeks after the final dose.

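### The TEAE cut-off of exactly 8 weeks after the final dose ends up to 2 days before a compliant End-of-Study Visit, so AEs starting on day +57 or +58 are left out of the primary safety tables

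*Protocol*

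**What the plan says.** Section 4.1 of the protocol names the primary safety variable: "Occurrence of TEAEs". Section 12.1.1 defines it by start date: "Treatment-emergent AEs are defined as AEs starting after the time of first IMP administration up to and including 8 weeks after the final dose". Section 14.3.1 applies the same limit. It states "Only TEAEs will be included in the summary tables", and "Adverse events starting before time of IMP administration or after 8 weeks after the final dose" appear in listings only. The definition and its analysis agree with each other.

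Section 8.4.8 sets the final visit: "The End-of-Study Visit will be conducted 8 weeks after the final dose". It then adds: "A visit window of ±2 days is applicable for this visit relative to the day of the final dosing visit". AEs are collected over the whole study, including the post-treatment period (Section 12.1.1), and are recorded at the End-of-Study Visit in every arm's schedule of assessments (Tables 5-1 to 5-5).

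No part of the protocol relates the TEAE limit to the visit window.

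**The concern.** The End-of-Study Visit is a visit at which new AEs can come to light. It has the only complete physical examination after Screening, the first ECG since day +7 and the first laboratory panel since day +42 (day +n means n days after the final dose). Section 12.8.5 requires clinically important new examination changes to be recorded as AEs, and the AE definition in Section 12.1.1 takes in abnormal laboratory findings.

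A finding with no known earlier onset may well be dated to the visit. Dated day +56, it is a TEAE. Dated day +57 at an equally compliant visit, it is not. Whether it counts in the primary variable then depends on a permitted scheduling difference of a day or two. A new physical examination finding in that position would be in no table at all, because Section 14.3.2 presents examination findings in listings only.

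**Working it through.** **1. Where the nominal final visit falls.** Scheduled days come from Tables 5-1 to 5-5. Post-dose day = End-of-Study day minus last dosing day.

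| Dose Arm | Last dosing day | End-of-Study day | Difference (days) |
|---|---|---|---|
| 1 | 29 | 85 | 56 |
| 2 | 15 | 71 | 56 |
| 3 | 8 | 64 | 56 |
| 4 and 5 | 1 | 57 | 56 |

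The stated 8 weeks (8 × 7 = 56 days) is reproduced in every arm.

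**2. The window against the cut-off.** Earliest compliant visit: 56 − 2 = day +54. Latest: 56 + 2 = day +58. TEAE limit: day +56, inclusive. The largest gap is 58 − 56 = 2 days, the same in all arms.

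**3. Which events are affected.**

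| Recorded start of AE | Found at a final visit on day +57 or +58 | Classification |
|---|---|---|
| By day +56 | Yes | TEAE, tabulated |
| Day +57 or +58 | Yes | Listed only |

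**4. Share of follow-up time.** 2/58 = 3.4% of post-dose time. Counted from the first dose, it is 2/86 = 2.3% in Dose Arm 1 and 2/58 = 3.4% in Dose Arms 4 and 5; the other arms lie between.

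**5. Rough effect on incidence.** The protocol gives no TEAE rate, so this is an illustration. Assume a constant hazard and a proportion q of subjects with at least one TEAE by the present cut-off, which is T days after the first dose (T = 84 in Dose Arm 1, 56 in Dose Arms 4 and 5). Then the hazard is h = −ln(1 − q)/T, and two more days add (1 − q) × (1 − exp(−2h)).

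| q | Added, T = 84 | Added, T = 56 |
|---|---|---|
| 30% | 0.6 percentage points | 0.9 |
| 60% | 0.9 | 1.3 |
| 80% | 0.8 | 1.1 |

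Even the largest value applied to the largest arm gives 15 × 0.013 = 0.2 subjects. A constant hazard may understate findings dated to the visit, since these cluster on one day. The protocol offers no figure with which to size that.

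**The case against.** A fixed post-dose window is a legitimate choice. It applies one limit to every subject and arm whatever the visit dates, it matches the 8-week Observation Period, and Sections 12.1.1 and 14.3.1 state it consistently. That any cut-off counts fewer events than a later one is not in itself bias. The TEAE analysis is descriptive, and no test or decision rule turns on these two days. All of this stands, and it is a reason to keep a fixed limit. It is not a reason to place that limit inside the window of the last scheduled visit.

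A reader might infer that everything first found at a late final visit drops out. The documents do not support this: classification goes by start date, and the AE question in Section 12.1.2 asks about the time since the last visit, so many events reported there will have started by day +56.

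A reader might also infer that 40% of final visits are affected, because 2 of the 5 window days lie past the cut-off. That is a share of calendar days. It becomes a share of visits only if visits spread evenly over the window, which nothing in the protocol supports, and it is not a share of events.

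Nor are the data lost. Excluded AEs are listed, and Section 14.3.2 summarizes laboratory, ECG and vital sign values by time point without regard to the TEAE limit.

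Finally, the protocol does not say that an unknown onset is dated to the visit. Completion of the AE form is left to the CRF Completion Guidelines (Section 12.1.3), and imputation of missing or partial dates to the SAP (Section 14.6). Dating to the visit is therefore a plausible practice, not a stated rule. The exclusion of any AE with a recorded start on day +57 or +58 does not depend on it.

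**Conclusion.** The mismatch is real and minor. AEs with a recorded start on day +57 or +58 are kept out of the TEAE tables although the protocol allows its own final AE assessment on those days. The affected time is at most 2 of 58 post-dose days. The likely effect is well under one subject per arm, given a constant hazard and an assumed TEAE incidence of 30% to 80%, and it is similar across arms. It does not threaten the safety conclusions. It is worth correcting because permitted scheduling should not decide whether a finding at the last visit counts in the primary variable.

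**What to change.** In Sections 12.1.1 and 14.3.1, set the TEAE limit at 8 weeks plus 2 days (58 days) after the final dose, in place of "up to and including 8 weeks after the final dose" and its counterpart. This covers every in-window End-of-Study Visit. A common fixed limit is better than one running to the actual visit date, which would let the window vary with scheduling when a visit is later than day +58.

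The cost is one phrase in each of two sections. The AE data are already collected. Reported TEAE incidence may rise slightly.
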